3.1. Overall Study Design and Plan

This is a Phase 2b, randomized, double-blind, placebo-controlled study evaluating the safety and efficacy of EFX in non-cirrhotic subjects with NASH. Subjects will be fibrosis stage 2 or 3 (F2-3) and dosed weekly with EFX or placebo.

Subjects meeting the study's eligibility criteria will be randomly assigned in a 1:1:1 ratio into 3 treatment groups as shown in Figure 2 below. Following 24 weeks of dosing, subjects will transition into the long-term safety follow-up portion of the study and will be followed until Week 96. If a subject refuses to complete the Week 24 liver biopsy, the subject will be discontinued from the study at Week 24. Only a 30-Day Follow-up visit is required following discontinuation of study drug. After all subjects have completed at least 52 weeks of treatment on their randomized dose, all subjects randomized to receive EFX will roll over into a single EFX dose arm (28 mg or 50 mg). The dose will be selected based on the Week 24 analysis and in alignment with regulatory authority.

Subjects on placebo will remain in the same treatment group for the duration of the study. After completing Week 96, subjects on placebo will be offered the option to receive EFX in a rollover study.

Figure 2. Study Schema

Randomization:

Randomization will be stratified by baseline type-2 diabetes status and fibrosis score. Study drug will be administered subcutaneously once weekly (QW). Eligible subjects will be randomized to one of three treatment groups with a ratio of 1:1:1.

- Group A: Placebo
- Group B: 28 mg EFX
- Group C: 50 mg EFX

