4.2. Inclusion Criteria

Subjects must meet all the following inclusion criteria to be eligible for study participation:

1. Males and non-pregnant, non-lactating females between 18 - 75 years of age inclusive, at the time of the screening visit.
2. Previous history or presence of 2 out of 4 components of metabolic syndrome (obesity, dyslipidemia, elevated blood pressure, elevated fasting glucose) or type 2 diabetes.
3. **Initial Screening Visit:** After a signed informed consent and confirmation of clinical risk profile associated with NASH, a screening lab panel and elastography will be measured for all subjects during an initial screening period:

- a. FibroScan® median liver stiffness > █

- b. CAP █

Note: All subjects must complete a FibroScan® examination during the screening period. However, the median liver stiffness and CAP inclusion criterion do not apply to subjects with an eligible historical liver biopsy performed \leq 180 days prior to randomization which confirmed fibrosis 1-3 and a NAS \geq 4.

If a historical value for FibroScan® is available in the past 3 months prior to the Screening Visit, then the FibroScan® does not need to be repeated.

- c. AST $>$ 17 for females and $>$ 20 for males;

Note: The AST inclusion criterion does not apply to subjects with an eligible historical liver biopsy performed \leq 180 days prior to randomization which confirmed fibrosis 2-3 and a NAS \geq 4.

- d. Estimated glomerular filtration rate (eGFR) \geq 60 mL/min, as calculated by the CKD-EPI equation;
- e. HbA1c \leq 9.5% (or serum fructosamine \leq 381 μ mol if HbA1c is unavailable);
- f. INR \leq 1.3, unless due to therapeutic anticoagulation;
- g. Direct bilirubin \leq ULN;
- h. Total bilirubin \leq upper limit of normal (ULN), unless due to an alternate etiology such as Gilbert's syndrome or hemolytic anemia;
- i. Creatinine kinase $<$ 3 x ULN;
- j. Platelet count \geq 140,000/ μ L;
- k. Triglyceride level \leq 500 mg/dL;
- l. ALT $<$ 5 x ULN;

- m. AST < 5 x ULN;
- n. ALP < 2 x ULN.

Note: Subjects meeting all of the above components will move into the next screening phase.

4. Documented historical stability (4 weeks to 6 months prior to screening) of ALT and AST levels showing no worsening at screening based on the following:
 - a. If the historical and screening ALT and AST values are both $\leq 1.5 \times$ the upper limit of normal (ULN), there is no limit to the difference between the values.

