5. MRI-PDFF [REDACTED]
Note: All subjects must complete an MRI-PDFF examination during the screening period. However, the MRI-PDFF inclusion criterion does not apply to subjects with an eligible historical liver biopsy performed ≤ 180 days prior to randomization which confirmed fibrosis 2-3 and a NAS ≥ 4 .
6. Biopsy-proven NASH. Must have had a liver biopsy obtained ≤ 180 days prior to randomization with fibrosis stage 2 to 3 and a non-alcoholic fatty liver disease (NAFLD) activity score (NAS) of ≥ 4 with at least a score of 1 in each of the following NAS components:
 - a. Steatosis (scored 0 to 3),
 - b. Ballooning degeneration (scored 0 to 2), and
 - c. Lobular inflammation (scored 0 to 3)
7. Subjects on Vitamin E ≥ 400 IU/day, thiazolidinediones (including, but not limited to, pioglitazone, rosiglitazone, and lobeglitazone), GLP-1 agonists, or SGLT2 inhibitors must be on a stable dose (defined as no significant change in prescription efficacy, initiation of medication, or medication discontinuation) for at least 3 months prior to the diagnostic liver biopsy through randomization. A switch from one drug to another in the same class should be discussed with the Medical Monitor to confirm eligibility.
8. Subjects on antidiabetic, weight loss, or lipid-modifying medication(s) must be on stable dose(s) for at least 3 months prior to the diagnostic liver biopsy through randomization.

9. Willing and able to give written informed consent prior to any study specific procedures being performed.
10. Female subjects of childbearing potential (see definition in [Appendix D](#)) must have a negative pregnancy test at screening and Baseline/Day 1.
11. Male and female subjects of childbearing potential who engage in heterosexual intercourse must agree to use protocol specified method(s) of contraception as described in [Appendix D](#).

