5.5 Safety Set

The analysis set for safety analyses will be the Safety Set which includes all subjects who received at least one dose of study drug.

All subjects who receive at least one dose of study drug will be included in the Safety Set. All safety endpoints will be summarized using the Safety Set and will be based on the actual treatment received if this differs from the randomized treatment. Some endpoints may be analyzed in additional populations or subgroups.

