7.1 General Principles

All data processing, summarization and analyses will be performed using Fortrea's SAS Environment / Version 9.4 (or later) of the SAS® statistical software package.

The following principles will be applied to all tables, figures, and listings (TFLs) unless otherwise stated:

Principle	Value
Significant tests	Two-sided and use a 5% significance level for main effects and 10% significance level for interaction terms.
Treatment group labels and order presented	Placebo EFX 28 mg EFX 50 mg All EFX (as applicable) Total (as applicable)
Tables	Data in summary tables presented by assessment or parameter, treatment group, and visit (where applicable).
Listings	All individual subject data will be listed as measured and presented by treatment group, subject, and visit (where applicable), unless otherwise specified.
Descriptive summary statistics for continuous variables	Number of non-missing values (n), arithmetic mean, arithmetic standard deviation (SD), median and range (minimum and maximum). Descriptive statistics for certain continuous data will include geometric mean and geometric coefficient of variation. PK concentrations will be summarized with the set of continuous parameters including geometric mean and will add the statistic of number of samples below the limit of quantification (BLQ).
Descriptive summary statistics for categorical variables	Frequency counts and percentages [n (%)].
Denominator for percentages	Number of subjects in the analysis set, unless stated otherwise in table shell.
Include "Missing" as category	Demographics and Other Baseline Characteristics only.

Statistical Analysis Plan

Sponsor Name: Akero Therapeutics, Inc.
Sponsor Protocol ID: AK-US-001-0102

Principle	Value
Display for 0 percentages	Blank
Display collected value	Minimum and maximum
Display 1 decimal place	Q1 (25 th Percentile), Q3 (25 th Percentile), Mean, Mean Difference, Median, Standard Deviation, and Confidence Interval for all parameters except DXA parameters.
Display 3 decimal places	Q1 (25 th Percentile), Q3 (25 th Percentile), Mean, Mean Difference, Median, Standard Deviation, and Confidence Interval for DXA parameters; p-value.
Limit of precision for displays	1 decimal place, unless otherwise specified.
Date Format	DDMMYYYY

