7.6.3.7 Changes in cardiovascular and metabolic risk factors

The analysis of changes in cardiovascular and metabolic risk factors will be performed using the Safety Set. Descriptive summaries and boxplots of BMI and blood pressure will be presented by treatment group and visit.

An MMRM model with baseline covariate will be used to evaluate the changes from baseline in blood pressure between the EFX arms and the placebo arm at scheduled visits, controlling for stratification factors. Least square (LS) means, 95% CIs, and p-values will be presented. The analysis will be performed using the Safety Set.

A CMH test will be used to compare the differences in proportions of subjects with new onset of T2D between the EFX arms and the placebo arm, adjusting for stratification factors. The new onset of T2D is defined as a single HbA1C value of 6.5% or higher when baseline HbA1c <6.5%. The analysis will be performed using the Safety Set.

7.6.3.8 Non-invasive measures of fibrosis can predict histological regression and/or progression of fibrosis and clinical complications of cirrhosis

Correlation models will be fitted to explore the correlation coefficient between non-invasive measures of fibrosis and histological fibrosis (CRN fibrosis stage of liver biopsy) and clinical complications of cirrhosis (MELD score and CP score). Non-invasive measures of fibrosis include serum biomarkers (ELF and Pro-C3) and imaging (liver stiffness by FibroScan). In addition, correlation between the imaging marker for hepatic fat (MRI-PDFF) and histological fibrosis and NASH resolution will also be explored. The analysis will be performed using the LBAS.

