7.6.5 Subgroup Analysis

Subgroup analysis will be performed for the efficacy endpoints (see [Table 4](#)). The group variables are as follows:

Statistical Analysis Plan

Sponsor Name: Akero Therapeutics, Inc.
Sponsor Protocol ID: AK-US-001-0102

- Baseline T2D (yes or no)
- Baseline fibrosis score (F2 or F3)
- Statin use at baseline (yes or no)
- Endogenous FGF21 at baseline (>median or ≤median)
- Pro-C3 at baseline (<14 µg/mL or ≥14 µg/mL)
- Baseline hypertension status (yes or no)
- BMI categories at Baseline (>median or ≤median)

Additional subgroups will be presented for the primary efficacy endpoint as follows:

- Age categories (<65 years, ≥65 years, ≥75 years)
- Ethnicity (Hispanic or Latino, not Hispanic or Latino)
- NAS at Screening (≤5, >5)
- Baseline liver fat (<10%, ≥10% to <20%, ≥20%)

Table 4 Summary of Subgroup Analysis

Endpoint	Subgroup
Primary: improvement in liver fibrosis (one stage) and no worsening of steatohepatitis at Week 24	LBAS subgroups: age category, ethnicity, NAS at Screening, baseline liver fat, baseline T2D, baseline fibrosis score, statin use at baseline, endogenous FGF21 at baseline, and baseline BMI category
Secondary: resolution of steatohepatitis and no worsening of liver fibrosis at Week 24 and 96	LBAS subgroups: baseline T2D, baseline fibrosis score, and statin use at baseline
Secondary: improvement in liver fibrosis (≥ one stage) at Week 24 and 96	LBAS subgroups: baseline T2D, baseline fibrosis score, and statin use at baseline
Secondary: change from baseline in hepatic fat fraction by MRI-PDFF at Week 24 and 96	MRI-PDFF Analysis Set subgroups: baseline T2D, baseline fibrosis score, statin use at baseline, and baseline liver fat
Secondary: improvement in liver fibrosis (one stage) and no worsening of steatohepatitis at Week 96	LBAS subgroups: age category, ethnicity, NAS at Screening, baseline liver fat, baseline T2D, baseline fibrosis score, statin use at baseline, endogenous FGF21 at baseline, and baseline BMI category
Secondary: lipoproteins (Lp (a), total cholesterol, triglycerides, Non-HDL-C, HDL-C, LDL-C and LDL-P) and markers of	FAS subgroups: statin use at baseline, baseline T2D, and baseline fibrosis score

CONFIDENTIAL

Statistical Analysis Plan

Sponsor Name: Akero Therapeutics, Inc.
Sponsor Protocol ID: AK-US-001-0102

Fortrea Study ID: 000000208791

Endpoint	Subgroup
lipid metabolism (ApoB and ApoC-III) change from baseline	

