Secondary: markers of glycemic control (HbA1c, C-peptide, Adiponectin and HOMA-IR) change from baseline	Biomarkers Analysis Set subgroups: baseline T2D and statin use at baseline
Secondary: serum fibrosis biomarkers (ELF, Pro-C3, C3M, NIS-4) change from baseline	Biomarkers Analysis Set subgroups: baseline T2D, baseline fibrosis score, and statin use at baseline for ELF, Pro-C3, C3M, and NIS-4; Pro-C3 at baseline for Pro-C3
Secondary: liver stiffness change from baseline	LBAS subgroups: baseline T2D, baseline fibrosis score, and statin use at baseline
Secondary: body weight change from baseline	FAS subgroups: baseline BMI category, baseline T2D, baseline fibrosis score
Exploratory: improvement in liver fibrosis (one stage) and resolution of steatohepatitis at Week 96	LBAS subgroups: age category, ethnicity, NAS at Screening, baseline liver fat, baseline T2D, baseline fibrosis score, statin use at baseline, endogenous FGF21 at baseline, and baseline BMI category
Exploratory: fibrosis stage and NAFLD Activity Score (NAS) on liver histology at Week 24	LBAS subgroups: baseline T2D and baseline fibrosis score
Exploratory: improvement in liver fibrosis (\geq two stages) and no worsening of steatohepatitis at Week 24 and two stage improvement in liver fibrosis at Week 24	LBAS subgroups: baseline T2D, baseline fibrosis score, and statin use at baseline
Exploratory: cardiovascular and metabolic risk factors (blood pressure)	Safety Set subgroup: baseline hypertension status
Exploratory: MRI-PDFF based quantitation of hepatic fat	MRI-PDFF Analysis Set subgroups: baseline T2D, baseline liver fat
Exploratory: health-related quality of life (CLDQ-NASH) change from baseline	FAS subgroups: baseline T2D

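### New-onset type 2 diabetes is defined by HbA1c alone, so a known diabetic with baseline HbA1c below 6.5% can be counted as a new case (exploratory endpoint)

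*SAP*

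**What the plan says.** SAP 7.6.3.7 compares each EFX arm with placebo on the proportion of subjects with new onset of T2D, using a CMH test adjusted for the stratification factors. The event rule is: "The new onset of T2D is defined as a single HbA1C value of 6.5% or higher when baseline HbA1c <6.5"%. The analysis set is the "Safety Set which includes all subjects who received at least one dose of study drug" (SAP 5.5). SAP Table 3 also assigns the incidence of T2D to the Safety Set, with no restriction. The default denominator in SAP 7.1 is: "Number of subjects in the analysis set, unless stated otherwise in table shell".

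On entry, Protocol 4.2 criterion 2 lists components of metabolic syndrome and ends "elevated blood pressure, elevated fasting glucose) or type 2 diabetes", so T2D is itself a route into the trial. Criterion 3e caps HbA1c at 9.5% and sets no lower limit. Criterion 8 reads: "Subjects on antidiabetic, weight loss, or lipid-modifying medication(s) must be on stable dose(s) for at least 3 months", so treated diabetics are eligible.

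T2D status is held separately from HbA1c. Protocol 3.1 says: "Randomization will be stratified by baseline type-2 diabetes status and fibrosis score". SAP 7.4 summarises T2D status at Screening, and SAP 7.6.5 lists "Baseline T2D (yes or no)" as a subgroup variable. For the metabolic risk factors, SAP Table 4 has only the row "Exploratory: cardiovascular and metabolic risk factors (blood pressure)", split by hypertension status.

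**The concern.** A subject can have new onset of a disease only if the disease was absent at the start. The SAP tests for that with baseline HbA1c alone, but a treated diabetic may well sit below 6.5%. The plan already has the variable that would separate the two groups and does not use it here.

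The error need not be equal between arms. Protocol 1.4.1.3 reports a significant Week 16 HbA1c reduction of 0.39 points at 50 mg. Protocol 1.7 says the effect of 28 mg on glycemic control appeared less, given only 16 weeks of treatment. If EFX lowers HbA1c, fewer known diabetics on EFX than on placebo will cross 6.5%, and better control of existing diabetes could be reported as prevention of new diabetes. That is a different clinical claim. Table 4 does not split the new-onset counts by T2D status, so the planned tables would not show where the cases came from.

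**Working it through.** The documents give no expected rate or count for this endpoint, so there is no figure to reproduce. The check has two parts.

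**1. Does the text allow the misclassification?** Take a subject with T2D at screening, on stable treatment, with baseline HbA1c 6.3% and one later value of 6.5%.

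- Eligible: yes (Protocol 4.2, criteria 2, 3e and 8).
- In the Safety Set: yes, once dosed (SAP 5.5).
- Meets the event rule: yes, 6.3 is below 6.5 and the later value is 6.5 or higher (SAP 7.6.3.7).
- Removed by stratification: no. The CMH test has a T2D-yes stratum. True new onset is impossible there, so every event counted in it is misclassified, and it is pooled into the result.

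A single value is enough, and SAP 6.1 has eight post-baseline windows for glycemic markers, so a subject near the threshold has several chances to cross.

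**2. How large could it be?** N = 40 per arm is from Protocol 5.2.2. Everything else here is an assumption: p is the share with T2D, q the share of those with baseline HbA1c below 6.5%, and x the share of that group who later cross 6.5%.

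| Quantity | Formula | Low p, q (0.3, 0.1) | High p, q (0.8, 0.5) |
|---|---|---|---|
| Known diabetics exposed to being counted | 40·p·q | 1.2 | 16 |
| Truly at risk, at most | 40·(1 − p) | 28 | 8 |
| Shrinkage of a true risk difference under the default denominator | 40·(1 − p)/40 | 0.70 | 0.20 |

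The first row is the exposed pool, not a forecast; only a fraction x of it becomes counted cases. The last row leaves the risk ratio for true new cases unchanged, provided the arms have the same T2D share.

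*Expected counts.* Take p = 0.5–0.7, q = 0.2–0.4, and true new onset in 5% of subjects without T2D.

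- True cases per arm: 40·(1 − p)·0.05 = 0.6 to 1.0.
- If x = 0.2 in every arm, false cases are 40·p·q·0.2 = 0.8 to 2.2 per arm, which is 44% to 79% of all counted cases.
- If x = 0.4 on placebo and 0.1 on EFX, the counted rate is 6.5–12.7% on placebo and 2.9–4.5% on EFX, although true onset is 5% of those at risk in both arms.

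*Single illustration.* Take p = 0.6 and q = 0.3.

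- With T2D: 40 × 0.6 = 24. Of these, below 6.5%: 24 × 0.3 = 7.2, about 7. At risk: 40 − 24 = 16.
- Suppose 1 true case in each arm, and 3 of 7 placebo against 1 of 7 EFX diabetics cross.
- Counted under the SAP rule: placebo (1 + 3)/40 = 10.0%; EFX (1 + 1)/40 = 5.0%. Risk difference −5.0 points, risk ratio 0.50.
- Stratified by T2D with Mantel-Haenszel weights 16·16/32 = 8 and 24·24/48 = 12: (8 × 0 + 12 × (−2/24))/20 = −0.05, again −5.0 points.
- Restricted to those at risk: 1/16 = 6.3% in both arms. Risk difference 0, risk ratio 1.00.

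If crossings were equal in both arms, the false cases would instead pull the risk ratio for a real difference towards 1.

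**The case against.** The strongest case on the other side concerns weight. This is one comparison within an exploratory item, and no visible text ties a decision to it. The rule is stated openly, individual data are listed, and HbA1c change is analysed by baseline T2D (SAP Table 4), so a careful reader could see what was counted. All of that is true. It limits the consequence, but the count would still carry the wrong label.

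The exploratory endpoint lists (SAP 3.3, Protocol 7.1.1.3) are not visible and the table shells are not supplied, so a restriction could sit there. The denominator point is therefore conditional. The numerator point rests on the operative definition in SAP 7.6.3.7, which contains no restriction.

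The illustration uses chosen counts and shows one direction. Stratified by T2D (fibrosis stage ignored), its CMH test gives p = 0.40, with an odds ratio of 0.48 (95% CI 0.08 to 2.74), so it would support no treatment claim. That is correct. It shows that the numbers are small; it does not show that stratifying removes the misclassified events, and the estimate still moves from no difference to −5 points. The contrast between 50 mg and 28 mg is only a plausible direction, since Protocol 1.7 qualifies it by the 16-week duration and this trial runs to Week 96.

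**Conclusion.** The concern holds. Followed exactly, SAP 7.6.3.7 counts known diabetics as new cases, and no visible text prevents it. The size cannot be fixed from the documents. Under the stated ranges, the pool open to misclassification can be as large as or larger than the group truly at risk, and with moderate assumptions about half to four fifths of counted cases would be known diabetics. A bias in favour of EFX is plausible but not established. The effect is confined to this exploratory comparison, so it is a correction that should be made rather than a threat to the trial's main results.

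**What to change.** Replace the definition in SAP 7.6.3.7 with text to this effect:

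> The new-onset T2D analysis includes Safety Set subjects with baseline T2D = No and baseline HbA1c <6.5%. These subjects form both the numerator's source and the denominator. New onset is a post-baseline HbA1c of 6.5% or higher. The CMH test for this endpoint is stratified by baseline fibrosis stage only.

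T2D status is constant in this set, so it drops out as a stratum. Crossings of 6.5% among subjects with baseline T2D can be tabulated separately, under a label that describes glycemic control rather than onset.

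The cost is a short text change and a filter on two variables already collected. SAP Version 3 is final and a sponsor team sees unblinded Week 24 results (SAP 7.9), so the change should be dated and recorded in SAP section 8. If the definition can no longer be replaced, the restricted analysis can be added as a supplementary one and the existing count relabelled. The downside is precision: with at most 8 to 28 subjects per arm at risk under the ranges above, an arm may have no events. The Fisher's exact fallback in SAP 7.6 is worded for histology responses and would need to be extended to this endpoint.
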